## **2.3 Rationale**

Clinical data has demonstrated that AS is sensitive to taxanes.(18-22) Indeed at our institution first line therapy is paclitaxel or gemcitabine with taxotere. However, all patients with advanced disease will eventually progress.

Eribulin, a novel microtubule-depolymerizing drug has shown clear activity in metastatic breast and sarcoma patients, despite failure of prior taxanes in many of these patients.

There is now emerging evidence in breast cancer models that Eribulin induces tumor vasculature remodeling as well as altering angiogenesis signaling pathways involved in endothelial cell-pericyte interactions as well as VEGF expression.(12) Moreover, there is further evidence of the Eribulin-mediated vascular remodeling hypothesis in PDX and human breast cancer patients where Eribulin can decreases tumor hypoxia.(23)

In addition to the above there are now anecdotal reports as well as a published report of angiosarcoma patients responding to Eribulin.(24)

Together these data suggest Eribulin's anti-tumor activity is through multiple mechanisms including microtubule targeting, alterations in angiogenesis signaling/vasculature remodeling and tumor hypoxia changes. Thus, we hypothesize that Eribulin will show anti-cancer activity in vascular malignancies including angiosarcoma and progressing epithelioid hemangioendothelioma.

## **2.4 Correlative Studies Background**

In this pilot study, we seek to determine if there are expression and/or genomic variations that correlate with mechanisms of response and/or resistance to Eribulin as a single agent in patients with metastatic or unresectable angiosarcoma. Tumor samples from core needle biopsies pre- and post-treatment will be analyzed by RNA seq and whole exome sequencing. Whole exome sequencing from cell free DNA (cfDNA) will be analyzed from peripheral blood from angiosarcoma patients.

The Broad Institute has sequenced exomes or genomes of over 5000 tumors and has also pursued RNA-seq in hundreds of tumors to discover gene fusions, splice isoforms, and mutations. The Institute has extensive experience in the application of genomics to studies of cancer drug response and resistance in multiple cancer types (Wagle, Emery et al, Journal of Clinical Oncology 2011(25); Van Allen, Wagle, et al, Cancer Discovery, 2014a(26); Wagle, Van Allen, et al, Cancer Discovery, 2014b; Wagle et al, Cancer Discovery, 2014c; Wagle et al, New England Journal of Medicine, 2014(27)). In addition, Broad teams have experience performing sequencing from small amounts of starting material. The Broad Institute now routinely generates WES and RNA-seq data using DNA/RNA obtained from a single core biopsy.

The proposed blood biopsy pilot will be performed in collaboration with [name], who leads the Blood Biopsy Team at the Broad Institute. [name] group consists of a multi-institutional collaboration that is focused on identifying mechanisms of response and resistance to therapies. His group has piloted an approach to performing WES of cfDNA obtained from blood biopsies in patients with metastatic breast cancer (Adalsteinsson et al, In Revision). These pilot efforts have been highly successful in demonstrating their ability to capture and sequence cfDNA. Using an efficient, low-cost method they have developed to assess purity of tumor-derived cfDNA, they found that 85.2% of 251 patients with ER+ MBC had greater than 3% purity of tumor-derived cfDNA and 40.6% had greater than 10%. They performed WES on cfDNA and matched metastatic biopsies from 15 of these patients. WES from cfDNA in these 15 patients identified 90% of the clonal mutations found WES from matched metastatic biopsies (on average; range 60-100%). WES from cfDNA detected 46% of the subclonal mutations identified in the metastatic biopsies (on average; range 10-87%). Copy number alterations were also highly concordant with matched metastatic biopsies, suggesting that cfDNA can also be used for copy number analysis. [name] has also shown that numerous tumor types can be studied by this method (verbal communication), which provides rationale for determining whether this method can be applied to studying cfDNA in angiosarcoma patients.

### **3. PARTICIPANT SELECTION**

#### **3.1 Eligibility Criteria**

- 3.1.1 Metastatic or locally advanced angiosarcoma, treated with at least one prior systemic therapy where no standard of care curable therapy is available OR metastatic or locally advanced malignant and progressive epithelioid hemangioendothelioma (EHE).
  - 3.1.1.1 A maximum of 5 EHE patients will be accrued on this study
- 3.1.2 Archival tissue confirming the diagnosis must be reviewed by BWH/DFCI/MGH pathology.
- 3.1.3 Progression on at least one prior systemic therapy or progression during an observation phase of no anti-cancer therapy within the prior 3 months; prior taxanes are allowed

3.1.4 Participants must have measurable disease by RECIST 1.1, defined as at least one lesion that can be accurately measured in at least one dimension (longest diameter to be recorded for non-nodal lesions and short axis for nodal lesions) as  $\geq 20$  mm with conventional techniques or as  $\geq 10$  mm with spiral CT scan, MRI, or calipers by clinical exam. See Section 11 for the evaluation of measurable disease.

3.1.5 Age  $\geq 18$  years.

3.1.6 ECOG performance status  $\leq 2$  (see Appendix A)

3.1.7 Life expectancy of greater than 3 months

3.1.8 Participants must have normal organ and marrow function as defined below:

- leukocytes	$\geq 3,000/\text{mcL}$
- absolute neutrophil count	$\geq 1,000/\text{mcL}$
- platelets	$\geq 100,000/\text{mcL}$
- total bilirubin	within normal institutional limits
- AST(SGOT)/ALT(SGPT)	$\leq 2.5 \times$ institutional upper limit of normal
- creatinine clearance	$\geq 50 \text{ mL/min}/1.73 \text{ m}^2$ for participants with creatinine levels above institutional normal.

3.1.9 Baseline QTcF  $<$  grade 2

3.1.10 The effects of Eribulin on the developing human fetus are unknown (Please also see exclusion criteria 3.2.6). For this reason and because of the risk of teratogenicity, women of child-bearing potential must agree to use adequate contraception prior to study entry and for the duration of study participation, and 4 months after completion of Eribulin administration. Should a woman become pregnant or suspect she is pregnant while she or her partner is participating in this study, she should inform her treating physician immediately. Men treated or enrolled on this protocol must also agree to use adequate contraception prior to the study, for the duration of study participation, and 4 months after completion of Eribulin administration. Please see section 5.6 for complete details on contraception.

3.1.11 Willingness to undergo serial tumor biopsies before and on treatment.

3.1.12 Ability to understand and the willingness to sign a written informed consent document.

## 3.2 Exclusion Criteria

- 3.2.1 Participants who have had chemotherapy or radiotherapy within 3 weeks (6 weeks for nitrosoureas or mitomycin C), immunotherapy within 3 weeks, targeted therapies (e.g. small molecule inhibitors such as pazopanib) within 2 weeks prior to entering the study or those who have not recovered from adverse events due to agents administered more than 4 weeks earlier. Not clinically significant or clinically stable adverse events from prior therapy (e.g. immunotherapy related hypothyroidism or insulin-dependent diabetes stable on medication or TKI-related hypertension or rash etc.) is allowed.
- 3.2.2 Participants who are receiving any other investigational agents.
- 3.2.3 Participants with with brain or subdural metastases are not eligible, unless they have completed local therapy and have discontinued the use of corticosteroids for this indication for at least 4 weeks before starting treatment in this study. Any signs (e.g. radiologic) or symptoms of brain metastases must be stable for at least 4 weeks before starting study treatment. Participants with leptomeningeal disease should be excluded from this clinical trial because of their poor prognosis and because they often develop progressive neurologic dysfunction that would confound the evaluation of neurologic and other adverse events.
- 3.2.4 History of allergic reactions attributed to compounds of similar chemical or biologic composition to eribulin.
- 3.2.5 Uncontrolled intercurrent illness including, but not limited to, ongoing or active infection, symptomatic congestive heart failure (NYHA Class II), unstable angina pectoris or myocardial infarction within 6 months of enrollment, serious or life-threatening cardiac arrhythmia, subjects with a high probability of Long QT syndrome or QTcF prolongation of  $\geq 501$  msec (grade 2) on at least two separate ECG following correction of any electrolyte imbalance or psychiatric illness/social situations that would limit compliance with study requirements.
- 3.2.6 Females who are breastfeeding or pregnant at Screening or Baseline (as documented by a positive beta-human chorionic gonadotropin [ $\beta$ -hCG] (or human chorionic gonadotropin [hCG]) test with a minimum sensitivity of 25 IU/L or equivalent units of  $\beta$ -hCG (or hCG)). A separate baseline assessment is required if a negative screening pregnancy test was obtained more than 72 hours before the first dose of study drug.
- 3.2.7 HIV-positive participants on combination antiretroviral therapy are ineligible because of the potential for pharmacokinetic interactions with Eribulin. In addition, these participants are at increased risk of lethal infections when treated with marrow-suppressive therapy. Appropriate studies will be undertaken in participants receiving combination antiretroviral therapy when indicated.

### 3.3 Inclusion of Women and Minorities

Both men and women of all races and ethnic groups are eligible for this trial.

## 4. REGISTRATION PROCEDURES

### 4.1 General Guidelines for DF/HCC Institutions

Institutions will register eligible participants in the Clinical Trials Management System (CTMS) OnCore. Registrations must occur prior to the initiation of protocol therapy. Any participant not registered to the protocol before protocol therapy begins will be considered ineligible and registration will be denied.

An investigator will confirm eligibility criteria and a member of the study team will complete the protocol-specific eligibility checklist.

Following registration, participants may begin protocol therapy. Issues that would cause treatment delays should be discussed with the Overall Principal Investigator (PI). If a participant does not receive protocol therapy following registration, the participant's registration on the study must be canceled. Registration cancellations must be made in OnCore as soon as possible.

### 4.2 Registration Process for DF/HCC Institutions

DF/HCC Standard Operating Procedure for Human Subject Research Titled *Subject Protocol Registration* (SOP #: REGIST-101) must be followed.

### 4.3 General Guidelines for Other Investigative Sites

N/A

### 4.4 Registration Process for Other Investigative Sites

N/A

## 5. TREATMENT PLAN

### 5.1 Treatment Regimen

Eribulin will be administered on day 1 and day 8 of a 21-day cycle. Treatment will be administered on an outpatient basis. Reported adverse events and potential risks are described in Section 7. Appropriate dose modifications are described in Section 6. No investigational or commercial agents or therapies other than those described below may be administered with the intent to treat the participant's malignancy.

Regimen Description					
Agent	Premedications; Precautions	Dose	Route	Schedule	Cycle Length

Eribulin	No premedication requirements	1.4 mg/m  administered directly or diluted in NS	IV over 2-5 minutes	Days 1 and 8	21 days
----------	-------------------------------	--	---------------------	--------------	---------

Prophylactic GCSF will be administered according to national guidelines or institution standard.

Body surface area (BSA) will be calculated using the Dubois formula on day 1 of each cycle or per institution standard of care.

## 5.2 Pre-Treatment Criteria

Prior to any study related testing, patients will sign the informed consent form and undergo medical evaluation to establish their baseline condition and determine eligibility. The following studies will be obtained within 30 days of enrollment for the purpose of baseline assessment:

Complete medical history and physical examination including:

- Complete medical history
- Documentation status of disease
- Documentation of prior therapies
- Documentation of current medications
- Complete physical examination, including vital signs and assessment of ECOG performance status
- Pre-existing conditions will be assessed and evaluated according to the NCI CTCAE v4.03 to establish the patient's baseline condition

Disease-Specific Laboratory Tests- Pathology and Tumor Imaging

- Confirm institutional review of diagnostic pathologic material
- Baseline tumor imaging studies will be either CT or MRI. The modality chosen for any individual patient will be the same throughout the duration of the study.

The following screening tests will be performed within 15 days prior to Day 1 of treatment:

- CBC with differential
- Chemistries: sodium, potassium, chloride, bicarbonate, BUN, creatinine, glucose, calcium, phosphorus, magnesium, total bilirubin, alkaline phosphatase, AST, ALT, total protein, albumin
- PT and PTT
- Urinalysis
- Urine or serum pregnancy test (for premenopausal women)
- ECG

## 5.3 Cycle 1, Day 1

Patients who have signed the informed consent form, completed the screening process, and met the criteria for enrollment will be entered into the trial and assigned an identification number. In addition the following will be performed:

- Certification that patient meets all inclusion and exclusion criteria and is able to comply with all requirements of the clinical trial
- Review concomitant medications since screening
- Perform physical examination with vital signs and ECOG performance status
- Laboratory testing – to be done if screening labs were done more than 7 days prior to Day 1. Patient will wait for the lab results on this day to re-confirm lab parameters for eligibility.
  - CBC with differential
  - Chemistries: sodium, potassium, chloride, bicarbonate, BUN, creatinine, glucose, calcium, phosphorus, magnesium, total bilirubin, alkaline phosphatase, AST, ALT, total protein, albumin
  - Urine or serum pregnancy test (for premenopausal women) if not performed within 7 days of cycle 1 day 1
- Required core or excisional biopsy 1 will occur after registration and prior to cycle 1 day 1.
- It is recommended to correct hypokalemia and hypomagnesemia prior to treatment
- Administer Eribulin cycle 1 day 1 if treatment criteria are met
- HOLD Eribulin administration if:
  - ANC <1000/mm^3
  - Platelets < 75,000/mm^3
- ECG does not need to be repeated if obtained before cycle 1 day 1, unless clinically indicated

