## **10. STUDY CALENDAR**

Scans and x-rays must be done  $\leq$ 4 weeks prior to the start of therapy. Screening laboratory tests and ECG will be performed within 15 days prior to the start of therapy. In the event that the participant’s condition is deteriorating, laboratory evaluations should be repeated within 48 hours prior to initiation of the next cycle of therapy. Laboratory testing must be repeated if done more than 7 days prior to day 1.

Assessments must be performed prior to administration of any study agent. Study assessments and agents should be administered within  $\pm$  3 days of the protocol-specified date, unless otherwise noted. Dosing delays beyond noted windows for non-clinical reasons (e.g. weather, holidays) are permitted with approval of the overall PI.

	Pre-study	Cycle 1			Cycle 2 and beyond			Off Study H
		Wk 1	Wk 2	Wk 3	Wk 4	Wk 5	Wk 6	
Eribulin A		X	X		X	X		
Informed consent	X							
Pathology Review B	X							
Demographics	X							
Medical Hx	X							
Concurrent Meds	X	X	X		X	X		
Physical Exam	X	X	X		X	X		X
Vital Signs including weight	X	X	X		X	X		X
Height	X							
ECOG PS	X	X			X			X
Laboratory testing C	X	X	X		X	X		X
ECG	X I				X I			
Adverse Event Evaluation		X	X	X	X	X	X	X
Tumor Measurements D	X	Every 6 weeks for the first 7 cycles (before C3, C5, C7) and then every 9 weeks onward (before C10, C13, etc)						
Urine or serum B-HCG E	X							
Required Biopsy F	X						X	
Blood sample for cfDNA G		X			X			
A- Eribulin will be administered of 1.4 mg/m2 as an IV infusion over 2-5 minutes on Days 1 and 8 of every 21-day cycle B- Pathology review any time prior to the study C- CBC/diff, chemistries (sodium, potassium, chloride, bicarbonate, BUN, creatinine, glucose, calcium, phosphorus, magnesium, total bilirubin, alkaline phosphatase, AST, ALT, total protein, albumin); urinalysis only required on prescreening testing and PT/PTT only required on prescreening testing and before Biopsy 2. Screening laboratory tests will be performed within 15 days prior to Day 1 of treatment D- The modality (e.g. CT, MRI) should be consistent through the protocol. The window is +/- 1 week for the first 3 sets of scans/imaging then +/- 2 weeks thereafter; baseline tumor measurements should be performed within 28 days prior to Day 1 of treatment								

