- E- Urine or serum beta-HCG Must be repeated if not performed within 72 hours of cycle 1 day 1
- F- Biopsy 1 will occur after registration and prior to C1D1. Biopsy 2 will occur prior to the first imaging and C3D1. Platelet count and PT/PTT required pre biopsy 2 or per institutional standards. When possible the biopsy should be multiple cores or excisional. If the biopsy is considered unsafe the requirement may be waived after discussion with the overall PI.
- G- cfDNA will be collected after registration (prior to C1D1) and every D1 thereafter
- H- See section 5.8 for AE and SAE follow-up.
- I- ECG monitoring only required for screening, C2D1 and C3D1 unless the criteria for continued monitoring are met as per section 6.3. ECG does not need to be repeated on C1D1 if obtained within 15 days of C1D1, unless clinically indicated.

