### 13.6.2 Evaluation of the Primary Efficacy Endpoint

All participants who received at least one dose of Eribulin will be included in the overall response rate analysis. All eligible participants included in the study must be assessed for response to treatment, even if the patient is ineligible or there are major protocol therapy deviations, following intent-to-treat.

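### Section 5.3 lets a pregnancy test up to 7 days old stand at first dose, although 3.2.6 and calendar footnote E require a repeat after 72 hours

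*Combined protocol and SAP*

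**What the plan says.** Four places in the protocol govern the timing of the pregnancy test before first dose.

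- **Section 5.2** lists the test among the screening procedures: "The following screening tests will be performed within 15 days prior to Day 1 of treatment". A negative result can therefore be up to 15 days old when the patient arrives for cycle 1 day 1.
- **Section 5.3** calls for a test that day in premenopausal women only "if not performed within 7 days of cycle 1 day 1". The line is a sub-item of the laboratory bullet, which is itself "to be done if screening labs were done more than 7 days prior to Day 1".
- **Section 3.2.6** makes a separate baseline assessment mandatory when a "negative screening pregnancy test was obtained more than 72 hours before the first dose of study drug".
- **Section 10, footnote E** says: "Urine or serum beta-HCG Must be repeated if not performed within 72 hours of cycle 1 day 1".

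Section 10 also carries a general laboratory rule, "Laboratory testing must be repeated if done more than 7 days prior to day 1". The panel in footnote C does not include hCG, so the calendar treats routine laboratory tests (7 days) and the pregnancy test (72 hours) separately. Nothing in the protocol says which section takes precedence.

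**The concern.** Section 5.3 is the list that staff work from on the dosing day, and its pregnancy-test line gives a longer window than the exclusion criterion and the calendar. A site that follows it in good faith would treat a five-day-old negative test as sufficient and give the first dose, although 3.2.6 and footnote E require a new test.

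The test guards against fetal exposure. Section 3.1.10 states the reason for caution: "because of the risk of teratogenicity, women of child-bearing potential must agree to use adequate contraception". A missed repeat matters most in the rare case where a pregnancy would have been found. Even without a pregnancy, each missed repeat is a deviation that the protocol's own wording brings about.

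The 7-day figure in 5.3 looks like the general laboratory window applied to the pregnancy test. That is an inference from the way Section 10 keeps the two rules apart; the protocol does not say so.

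**Working it through.** The plan gives no figure of its own to reproduce. The check compares the rules by the age of the last negative test at first dose, reading the pregnancy-test line in 5.3 on its own.

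| Age of last negative test | 5.3 | 3.2.6 | Footnote E |
|---|---|---|---|
| 72 h or less | no repeat | no repeat | no repeat |
| more than 72 h, up to 168 h | **no repeat** | repeat | repeat |
| more than 168 h | repeat | repeat | repeat |

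The rules disagree only in the middle row.

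**Width of the gap**
- 7 days × 24 = 168 h; 168 − 72 = 96 h.
- Share of the window that 5.3 accepts: 96 / 168 = 57.1%.
- Share of the 15-day screening window in 5.2: 96 / (15 × 24) = 96 / 360 = 26.7%.

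**How many women might fall in it.** The protocol does not give the number of premenopausal participants. It is probably small among 16 patients, since Section 2.1 puts peak angiosarcoma incidence in the seventh decade. Assume 1, 3 or 5 such women, with screening test dates spread evenly over the 15 days:
- 1 × 0.267 = 0.27
- 3 × 0.267 = 0.80
- 5 × 0.267 = 1.33

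These are expected numbers of women whose test date falls in the gap. They are not expected numbers of missed tests, because some sites will apply 3.2.6 or footnote E. Actual scheduling could put none or all of the women in the gap.

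**Does anything else in the protocol close the gap?**
- The first item in 5.3 requires certification against all inclusion and exclusion criteria, which brings in 3.2.6. This is a real but partial safeguard, because the same list then gives a different instruction for this test.
- The cycle 1 day 1 hold criteria in 5.3 cover only neutrophils and platelets.
- Section 8.1.8 refers back to 5.2 for the criteria to be met before infusion, and 5.2 carries the 15-day window.
- The calendar grid marks the hCG test only in the pre-study column; the 72-hour repeat appears only in the footnote.

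**Effect on the primary analysis.** Section 13.6.2 states: "All participants who received at least one dose of Eribulin will be included in the overall response rate analysis". A woman dosed without the repeat stays in that analysis, so the denominator changes by 0. Section 13.4 defines the rate among eligible patients. A missed repeat does not make a woman ineligible unless she is pregnant or breastfeeding, so the same holds there for every other woman.

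**The case against.** The strongest reply is that the rules can all be obeyed at once. Section 5.3 says when a test must be done; it does not say that a repeat is unnecessary between 72 hours and 7 days. Where 5.3 means to waive a repeat, as for the ECG, it says so. A site that applies the 72-hour rule satisfies every section, so no order of precedence is needed. A lapse would require staff to overlook an exclusion criterion, a calendar footnote and the certification item. Section 4.1 adds an eligibility checklist, although that is tied to registration, which may come before the last 72 hours. Any woman in the gap has a negative test at most 7 days old and must have agreed to contraception (3.1.10 and 5.6). The expected counts rest on assumed numbers and timing.

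Much of this stands. The stricter rule does satisfy all the sections, the clinical risk per patient is low, and the counts are only illustrative. None of it corrects the instruction in 5.3. A reader of a conditional line takes it that no test is needed when the condition is not met, and here that reading breaches an exclusion criterion. The safeguards make a lapse less likely but do not remove the conflict.

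**Conclusion.** The concern holds. The current text of 5.3 conflicts with 3.2.6 and with footnote E for a negative test more than 72 and up to 168 hours old, and following 5.3 alone would omit a required pre-dose test. Two of the three repeat rules, including the exclusion criterion, agree on 72 hours, so 5.3 is the one to change.

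The 96-hour gap follows directly from the text. The figures of 0.3 to 1.3 women depend on the assumed 1 to 5 premenopausal participants and the assumed even spread of test dates; the conclusion does not depend on them. The consequence is a safety-procedure deviation. Sample size, power and error rates are unaffected. It should be corrected because the potential harm is serious and the remedy is trivial.

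**What to change.** In Section 5.3, take the pregnancy test out of the 7-day laboratory bullet and give it its own line: premenopausal women have a urine or serum test if the last negative result was obtained more than 72 hours before the first dose. Leave 3.2.6 and footnote E as they are. The span over which the rules disagree then falls from 96 hours to 0.

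Moving the line also matters because, as now nested, the pregnancy test could be read as applying only when the routine screening laboratory tests are out of date.

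The cost is one line of wording and at most one repeat urine or serum test per affected patient, which 3.2.6 and footnote E already require.
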